8.11.1 Open-label eltrombopag treatment

The following patients will be eligible for open-label eltrombopag treatment:

- Patients randomized in the control arm (ATGAM + CsA without eltrombopag) who:
 - Show no hematological response at 6 months;
 - Do not demonstrate any clonal evolution at 6 months (as confirmed by bone marrow karyotyping);

(See section 12 for related methodological issues)

All these patients are eligible to receive a course of eltrombopag; at judge of the investigator, eltrombopag will be offered as either:

- Single agent treatment;
- Eltrombopag associated with second course of immunosuppression (without any restriction concerning the anti-lymphocyte agent).

Eltrombopag treatment will be started at the same dose of 150 mg/day, and will be continued for 3 months in case of complete response at 3 months from re-introduction, or up to 6 months. After these 6 months of treatment, eltrombopag will be discontinued in any case independently from hematological response; the patients will continue the follow up, as prescribed per protocol (see paragraph 7.2).

8.12 Tapering and discontinuation of treatment

All patients will be treated according to the assigned treatment and dose adjustments described above for at least 1 year; starting from this time point patients showing stable response (at least 30 days) will taper their treatment according to established guidelines [32]. Cyclosporin A may be discontinued after slow tapering in the next 6-12 months (about 10%

per month); thus, patients should remain on CsA treatment for at least 18 months before withdrawal. In case of decrease on blood counts, the investigator may re-institute or re-escalate CsA therapy at his/her discretion.

9. Assessment of Efficacy

9.1 Definition of hematological response

Hematological response will be assessed at 3, 6, 12, 18 and 24 months from treatment starting; hematological response has to be demonstrated by a minimum of 3 determinations over a period of at least 2 weeks, starting at least 2 week after last transfusion. The first time patients will obtain remission will be considered as timepoint. The investigator will classify hematological response into complete, partial and no response as follows, according to NIH criteria [17].

For the main endpoint (section 9.6.1) a valid response has to be measured between month 3 minus 10 days and month 3 plus 10 days; in case of more than one measurement available in this time period, the best response will be taken.

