8.9.1 G-CSF

G-CSF will not be used routinely in the patients enrolled in this study; however, its use is allowed in particular clinical conditions which at judge of the investigator may take advantage of G-CSF, such as infectious complications in patients with severe neutropenia.

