9.1.1 Complete response (CR)

Patients will be considered as complete responders (CR) if achieving all the following:

- Following peripheral blood counts:
 - Hemoglobin >10 gr/dL
 - Absolute neutrophils >1.0 x 10⁹/L
 - Platelets >100 x 10⁹/L
- No evidence of clonal evolution (by marrow cytogenetic and flow cytometry, see below 9.5)

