9.6 Statistical criteria and definition of endpoints

9.6.1 Response rate (main endpoint)

The primary analysis will evaluate complete response rate at 3 months from randomisation in an intent-to-treat (ITT) population containing all randomized patients. A valid response has to be measured at month 3 plus and minus 10 days; in case of more than one measurement in this period, the best response will be taken. Death before 3 months will be considered a failure (i.e. no response). We expect a very limited number of cases alive at 3 months and non-evaluable, or withdrawals before 3 months; these cases will be excluded from the primary analysis, and sensitivity analyses will be performed to check the validity of conclusions.

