12.1 Sample Size Justification

This is a superiority study aiming to increase the 3-months complete response (CR) rate. CR rate after standard immunosuppression with hATG+CsA is estimated to be below 10%, and equal to 7% in a recent study from the NIH[17]. The sample size is calculated on the hypothesis that the experimental arm will increase the 3-months response rate up to 21% (by 3 folds, based on the 7% reported in Scheinberg et al [17]). In these conditions, the sample size to reject the null hypothesis at 5% significance level and with 80% power (two-sided test) is n=96 patients for each treatment arm (in total 192 patients). Calculations are based on the Pass2000 algorithm for differences of percentages in two independent samples. The sample size will be increased by 4% to compensate for possibly not evaluable patients for a total number of 200 patients to be enrolled (100 each treatment arm).

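### The month-3 complete-response rule does not settle whether confirmation applies, and as worded in 9.6.1 extra unscheduled counts can only raise a patient's chance of success

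*Protocol*

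**What the plan says.** Section 9.1 opens with a general rule: "hematological response has to be demonstrated by a minimum of 3 determinations over a period of at least 2 weeks", the first of them at least two weeks after the last transfusion. It dates a response from the first time remission is reached. It also says who decides: "The investigator will classify hematological response into complete, partial and no response".

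The second paragraph of 9.1 turns to the main endpoint. It sets a window of month 3 plus or minus 10 days and adds that "in case of more than one measurement available in this time period, the best response will be taken". Section 9.6.1 repeats this: "A valid response has to be measured at month 3 plus and minus 10 days", again with the best response taken. It mentions neither confirmation nor a transfusion-free interval.

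Sections 9.6.2, 9.6.3 and 9.6.4 (time to first, best and complete response) each require confirmation in at least three consecutive determinations.

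Appendix 2 schedules hematology at months 2, 2.5, 3 and 4, with one schedule for both arms. Section 3 describes the trial as open label.

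The CR definition also varies. The synopsis, 4.1 and 5.1 give three blood-count limits only. Section 9.1.1 adds the absence of clonal evolution on marrow.

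**The concern.** This rule decides who is a success on the only primary endpoint. A patient with one CR-level count among three in the window is CR if 9.6.1 is read alone and not CR if the three-determination rule of 9.1 governs. Because 9.6.2 to 9.6.4 restate the confirmation and 9.6.1 does not, one reader may conclude that it was dropped for the primary endpoint and another that it applies by default.

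Under the 9.6.1 wording, the number of counts taken in the window matters. Taking the best of several can never lower a patient's classification, so the CR rate rises with sampling frequency without any drug effect. Sites know the arm and classify the response. If they sample one arm more often, that arm gains. The sensitivity analyses in 12.6 deal with non-evaluable and excluded patients and would not reveal this.

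**Working it through.** **1. Visits inside the window.** With months of 30.44 days, month 2 is day 61, month 2.5 day 76, month 3 day 91 and month 4 day 122. The window is days 81 to 101. Month 2.5 lies about 15 days before month 3 and month 4 about 30 days after, so only the month-3 visit is scheduled inside. A second or third count inside it must be unscheduled.

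**2. The plan's own figure.** Section 12.1 states that the size needed to reject "the null hypothesis at 5% significance level and with 80% power (two-sided test) is n=96 patients for each treatment arm", for CR rates of 7% and 21%. With p1 = 0.07, p2 = 0.21 and mean 0.14:

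n = [1.960·√(2·0.14·0.86) + 0.842·√(0.07·0.93 + 0.21·0.79)]² / 0.14² = 95.2, so 96 per arm.

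The figure reproduces. Approximate power is 0.803; exact binomial power is 0.82.

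**3. CR rate under each reading.** The documents give no within-patient variability, so this is an assumption: each count is a latent normal variable with common within-patient correlation, and the threshold is met by 7% (or 21%) of single counts. Integrating over the patient effect gives:

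| Correlation | Best of 2 | Best of 3 | Three of three |
|---|---|---|---|
| 7%, 0.80 | 10.3% | 12.5% | 2.6% |
| 7%, 0.90 | 9.4% | 10.8% | 3.7% |
| 7%, 0.95 | 8.7% | 9.7% | 4.6% |
| 21%, 0.80 | 28.3% | 32.7% | 10.7% |
| 21%, 0.95 | 24.6% | 26.6% | 15.7% |

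A different model points the same way. Let a fraction f of patients fluctuate around the limits, each of their counts meeting CR independently with probability q, and let s = 0.07 − f·q be stable responders. Best of k is s + f·(1 − (1 − q)^k); three of three is s + f·q³. For f = 0.10 and q = 0.3, s = 0.04. Best of 1, 2 and 3 is then 7.0%, 9.1% and 10.6%, and three of three is 4.3%.

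**4. False positives if sampling differs by arm.** Assume no drug effect, a control rate of 7% from one count, and a gain of 4 points (7% to 11%, correlation about 0.90) for each eltrombopag patient with three counts. The test is an unstratified pooled z-test at 100 per arm, enumerated exactly, counting rejections that favour eltrombopag:

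- none extra-sampled: 7% v 7%, 2.5%
- 20% extra-sampled: 7% v 7.8% (7 + 0.2·4), 4.0%
- 50% extra-sampled: 7% v 9% (7 + 0.5·4), 7.6%
- all extra-sampled, no control: 7% v 11%, 16.8%

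The planned analysis is a stratified Mantel-Haenszel odds ratio, so these figures are approximate for it.

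**5. If confirmation is kept.** If it lowered both rates by 20% (5.6% v 16.8%), approximate power at 96 per arm would be 0.694 and n would be 124. Under the model in step 3 (2.6% v 10.7% up to 4.6% v 15.7%), exact power is about 64% to 75%, against 82% for 7% v 21%. The protocol does not say which reading the 7% was measured under.

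**The case against.** The strongest reply is that 9.1 can be read as a whole. Its first paragraph says what a response is and its second says when it must hold for the main endpoint. The text speaks of the best response, not the best count, and a response may already have to be confirmed. Nothing requires all three determinations to lie inside the window: months 2, 2.5 and 3 are scheduled and span more than two weeks. Three counts over 14 days would even fit in a 20-day window. This stands as far as it goes. The two rules are compatible under one reading, so a reader who infers that they cannot both be met goes too far. What remains is that the protocol does not state that reading, and that 9.6.1 omits the confirmation its neighbouring sections include.

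Several further inferences are tempting and not supported:

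- **That the trial is biased towards eltrombopag.** Appendix 2 gives both arms one schedule, and no sampling rates by arm are given. The 17% figure needs three counts in every eltrombopag patient and one in every control. At a correlation of 0.98, best of three is 8.7%, not 11%.
- **That the continuation rule pushes sites to find CR.** Under 8.1.1.2, CR at month 3 stops eltrombopag, while partial or no response continues it. The incentive could run either way. The weekly platelet counts after stopping (8.3.1) follow a CR already called in these patients.
- **That the clonal criterion cannot be assessed at month 3.** Appendix 2 requires a marrow then in case of CR. Under 9.5 leukemia or MDS does not need a second specimen, and an isolated abnormality not yet confirmed simply does not meet the definition.
- **That the lack of a G-CSF-free interval is an error.** Section 8.9.1 rules out routine use and otherwise says "its use is allowed in particular clinical conditions which at judge of the investigator may take advantage of G-CSF". Nothing in the protocol conflicts with that.

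**Conclusion.** The point holds as an unresolved rule for the primary endpoint. The protocol does not say whether the confirmation and transfusion-free requirements of 9.1 govern the month-3 CR, or which visits may supply the confirming counts. Under the 9.6.1 wording, extra unscheduled counts can only raise the chance of CR. In an open-label trial with investigator classification, this exposes the comparison to bias if sampling differs by arm. A difference is possible and is not shown.

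The size is illustrative and rests on the assumed correlation, the 7% single-count rate and the assumed share of extra-sampled patients. A nominal 7% could read anywhere from about 2.6% (three of three) to 12.5% (best of three). The one-sided error is about 4% to 8% for moderate imbalance and near 17% only at the extreme. The stated sample size is arithmetically correct, but the 7% v 21% assumption cannot be tied to a definition until one is fixed.

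**What to change.** Write one identical rule in 9.1 and 9.6.1:

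1. Replace the best-response clause with the determination nearest the month-3 target date within the window, the same in both arms, with a tie rule.
2. State whether the three-determination and transfusion-free requirements apply to the primary endpoint. If they do, name the counts that may confirm it, including any outside the window.
3. Derive CR by program, blind to arm, from the recorded counts and transfusion dates.
4. Report the other reading as a sensitivity analysis.
5. Reconcile the counts-only CR definition in the synopsis, 4.1 and 5.1 with 9.1.1, which adds the clonal criterion.

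This costs protocol wording and programming, and CR rates will be somewhat lower than under best-of-window. If confirmation is kept, the 7% v 21% assumption and the stated 80% power should be checked against the confirmed definition. Requiring CR at each of months 2, 2.5 and 3 is not recommended as a default. It would demand CR from about day 61, and with the two-week interval no transfusion from about day 47 (61 − 14). That is a different endpoint from CR at 3 months and, on the illustration above, a less powerful one.

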9.1.1 Complete response (CR)

Patients will be considered as complete responders (CR) if achieving all the following:

- Following peripheral blood counts:
 - Hemoglobin >10 gr/dL
 - Absolute neutrophils >1.0 x 10⁹/L
 - Platelets >100 x 10⁹/L
- No evidence of clonal evolution (by marrow cytogenetic and flow cytometry, see below 9.5)

9.1.2 Partial response (PR)

Patients will be considered as partial responders (PR) if achieving **all** the following:

- No longer meet criteria for diagnosis of SAA
- Transfusion independence (defined as no need of any PRBC or platelet transfusion)
- Peripheral blood counts:
 - Hemoglobin >8 gr/dL
 - Absolute neutrophils >0.5 x 10⁹/L
 - Platelets >20 x 10⁹/L

9.1.3 No response (NR)

Any patient not meeting any of the response criteria defined above will be classified as a non-responder.

9.2 Definition of CsA-dependent and CsA-independent hematological response

Starting from day 365 from the beginning of treatment, responses will be also classified according to the possibility to taper off cyclosporin A. The same classification described above will be utilized, with the addition of the prefix CsA independent (CI) or CsA dependent (CD). For instance, complete responders at day 365 will subsequently classified at the following visit as CD-CR or CI-CR if they still require or do not require drugs to sustain response, respectively. Based on the guidelines [32] which suggest a monthly 10% tapering of therapeutic CsA, a patient will qualify for CI-CR if he is able to achieve a CsA dose reduction of at least 25% at 15 months, 50% at 18 months, 75% at 21 months and 100% (CsA discontinuation) at 24 months, providing no hematological relapse has occurred.

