5.2 Secondary Endpoints

1. Time to first hematological response (complete or partial) described by a cumulative incidence curve (see paragraph 9.6)
2. Time to best hematological response, described by a cumulative incidence curve (see paragraph 9.6)
3. Time to complete response (see paragraph 9.6)
4. Rates of hematological response (overall, complete, partial) at 6, 12, 18 and 24 months
5. Overall survival (OS) probability; OS is defined as time from randomisation to death, or last follow-up for patients alive
6. Event-free survival (EFS) probability; EFS is defined as time from randomisation to either relapse, death, treatment failure or clonal evolution (whichever occurs first), or last follow-up for patients alive in response
7. Cumulative incidence of relapse, from first hematological response (complete or partial) (see paragraph 9.6)
8. Cumulative incidence of clonal evolution (as defined below, see 9.5): AML, MDS or karyotypic abnormalities (see paragraph 9.6)
9. Cumulative incidence of PNH population occurrence and clinical hemolytic PNH occurrence (see paragraph 9.6)
10. Cumulative incidence of discontinuation of immunosuppressive therapy
11. Rate of CsA-independent hematological response at 24 months
12. Need for transfusions (packed red cell units and platelet units) and number of transfusions required from treatment.
13. Need for any supportive care, including hospitalization
14. Quality of life (as assessed by the validated EORTC QLQ-C30 questionnaire)(changes over time and differences between treatment arms)
15. Safety and tolerability of the investigational treatment, including SAE

6. Patient Selection and Withdrawal

All patients must meet all of the inclusion criteria and none of the exclusion criteria listed below. Protocol waivers are not acceptable in this trial.

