8.1.1.3 Re-introduction of eltrombopag

For patients achieving hematological response (either complete or partial) who have discontinued eltrombopag, the agent can be re-introduced in case of relapse (see paragraph 9.3) or lack of robustness of hematological response occurring **within 6 months from discontinuation of eltrombopag**.

The following patients are eligible for re-introduction of eltrombopag within this study:

- Patients in CR at 3 months, who have discontinued eltrombopag as per protocol, with subsequent relapse (defined as no longer meeting the criteria of CR);
- Patients who have discontinued eltrombopag at 6 months as per protocol, and:
 - Were in CR at 6 months, with subsequent relapse (defined as no longer meeting the criteria of CR);
 - Were in PR at 6 months, with subsequent relapse (defined as no longer meeting the criteria of PR);
 - Were in PR at 6 months, with subsequent lack of robustness of their PR, defined as follows (any of these):
 - Drop in Hb >2 gr/dL (with Hb <10 gr/dL);
 - Drop >50% in ANC (with ANC <1,000/ μ L);
 - Drop >50% in Plt count (with Plt <50,000/ μ L).

In all these circumstances the second course of eltrombopag treatment will be started at the same dose of 150 mg/day, and will be continued for 3 months in case of complete response at

⁷ A study in 40 healthy volunteers showed that the co-administration of single dose eltrombopag 100 mg with repeat dose LPV/RTV 400 /100 mg twice daily resulted in a reduction in eltrombopag plasma AUC_(0-∞) by 17 % (90 % CI: 6.6 %, 26.6 %). Therefore, caution should be used when co-administration of eltrombopag with LPV/RTV takes place. Platelet count should be closely monitored in order to ensure appropriate medical management of the dose of eltrombopag when lopinavir/ritonavir therapy is initiated or discontinued.

3 months from re-introduction, or up to 6 months. After these additional 6 months of treatment, eltrombopag may be continued outside the protocol by the physician in charge of the patients but won't be furnished anymore by Novartis. Patients with transient falls in blood counts secondary to infectious complication or any other medical conditions do not qualify for re-introduction of eltrombopag. Similarly, patients with late relapses (>6 months from eltrombopag discontinuation), at time of CsA tapering or discontinuation, do not qualify for re-introduction of eltrombopag within this study.

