9.6.10 Other secondary endpoints

Other secondary endpoints (CsA-independent hematological response at 24 months, Need for transfusions, Need for any supportive care including hospitalization, safety and tolerability) will be described by standard summary statistics (frequency tables for categorical variables, mean with standard deviations and quantiles for continuous variables).

10. Assessment of Safety

A trial specific Safety Monitoring Plan is included in appendix 5. In this trial, safety will be determined through the collection of Adverse Event (AE) data, laboratory tests, etc.

Timepoints are listed in the flowchart (appendix 3).

The reference safety information (RSI) for Eltrombopag is the SmPC. The RSI for ATGAM is the USPI.

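### The CsA-independent response rule ignores eltrombopag, so a responder off CsA but still taking eltrombopag can be reported as not needing drugs

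*Protocol*

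**What the plan says.** Section 9.2 classifies responses from day 365 as CsA-dependent or CsA-independent. It explains the distinction by asking of responders "if they still require or do not require drugs to sustain response". The working rule is then that "a patient will qualify for CI-CR if he is able to achieve a CsA dose reduction of at least 25% at 15 months", with 50% at 18 months, 75% at 21 months and complete discontinuation at 24 months, "providing no hematological relapse has occurred". Eltrombopag is not mentioned.

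The rule feeds secondary endpoint 11 in section 5.2: "Rate of CsA-independent hematological response at 24 months". Sections 9.6.10 and 12.3 have it summarised descriptively.

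Section 8.1.1.3 lets responders who have stopped eltrombopag restart it within six months, for up to six more months. It adds: "After these additional 6 months of treatment, eltrombopag may be continued outside the protocol by the physician in charge of the patients". For rescued control patients, section 8.11.1 says: "After these 6 months of treatment, eltrombopag will be discontinued in any case independently from hematological response".

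**The concern.** The stated idea and the working rule in section 9.2 do not match. The idea is whether drugs are still needed to hold the response; the rule looks at CsA and relapse only. The investigational drug is itself an AA treatment that some patients may be taking when classified. If eltrombopag takes over from CsA in such a patient, the rule records independence.

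Endpoint 11 is where a reader would look for evidence that adding eltrombopag leads to a response that lasts without maintenance treatment. The protocol provides more room for late eltrombopag in the experimental arm than in the control arm, so any misclassification would tend to favour the experimental arm. Because the endpoint is only described, no model or test stands between the definition and the reported figure.

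**Working it through.** **1. Who can restart eltrombopag and still pass the relapse condition?** Section 9.2 does not define haematological relapse, and two definitions are available. Section 8.1.1.3 treats loss of CR (or of PR, for a patient in PR at month 6) as relapse. Section 9.3 defines clinical relapse by SAA criteria, transfusion need, or specified falls in neutrophils or platelets; it has no haemoglobin threshold.

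- *PR restarted for lack of robustness.* Suppose a patient in PR at month 6 falls from Hb 10.5 to 8.3 g/dL without transfusion. The drop is 10.5 − 8.3 = 2.2, above 2, with Hb below 10, so section 8.1.1.3 allows a restart. Hb is still above 8, so PR can be kept (9.1.2). This is not relapse under either definition.
- *Loss of CR.* A fall in platelets from 110 to 90 × 10⁹/L ends CR and allows a restart. Section 8.1.1.3 calls it relapse; section 9.3 does not. Whether the patient is excluded depends on which definition section 9.2 intends.
- *PR restarted for a neutrophil or platelet fall.* These thresholds nearly repeat section 9.3, so most such patients would probably be excluded if the fall is confirmed as 9.3 requires.

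I read the CsA steps, written for CI-CR, as applying to CI-PR too, because section 9.2 puts the prefix on the whole response classification.

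**2. When can eltrombopag be on board?** Latest in-protocol month = stop of first course + restart window + length of second course.

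- Stopped at month 6: 6 + 6 + 6 = 18, which reproduces the 18 months in section 7.2.3.
- Stopped at month 3 in CR: 3 + 6 + 6 = 15.
- Control rescue started at month 6: 6 + 6 = 12.

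| Route | 15 m | 18 m | 21 m | 24 m |
|---|---|---|---|---|
| Experimental, stopped at month 6 | possible | limit only | no | no |
| Experimental, stopped at month 3 | limit only | no | no | no |
| Control rescue from month 6 | no | no | no | no |
| Experimental, off-protocol continuation | possible | possible | possible | possible |

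For a patient who stopped at month 6, a full six-month course reaches month 15 only if restarted at month 9 or later (15 − 6 = 9). It reaches month 18 only if restarted at month 12, the end of the window. At month 24 an in-protocol second course has been over for at least 24 − 18 = 6 months, so only off-protocol use can affect endpoint 11.

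**3. How large could it be?** The documents give no figure for off-protocol use. As an assumption, take 100 patients per arm, the same true CsA-independent rate p in both arms (10% to 30%), and a share x of the experimental arm classed as independent only because of eltrombopag. The apparent gap is x, and

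OR = [(p + x)/(1 − p − x)] / [p/(1 − p)].

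For p = 0.10 and x = 0.05: (0.15/0.85)/(0.10/0.90) = 1.59. For p = 0.30 and x = 0.05: (0.35/0.65)/(0.30/0.70) = 1.26.

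| x | Apparent gap | OR for p from 30% to 10% |
|---|---|---|
| 2% | 2 points | 1.10 to 1.23 |
| 5% | 5 points | 1.26 to 1.59 |
| 10% | 10 points | 1.56 to 2.25 |

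These values show sensitivity to x. They do not estimate it.

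**The case against.** The strongest reply is that the endpoint measures what its name says. Section 9.2 opens with whether cyclosporin can be tapered, and the reference to drugs in general sits in an illustrative sentence. That is fair as to intent, but the sentence still tells the reader what the labels mean, and the rule does not deliver it.

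Several stronger readings are tempting, and the documents do not support them.

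- *That CsA dose alone decides.* The same sentence requires absence of relapse, which excludes a good part of those who restart eltrombopag. It does not exclude all of them.
- *That a second in-protocol course props up the 24-month endpoint.* It has ended by month 18.
- *That only the experimental arm can be on eltrombopag late.* Section 8.11.1 sets no latest start for control rescue, and section 8.11 leaves second-line treatment to the investigator. The imbalance lies in what the protocol provides and is not absolute.
- *That late CR and PR rates are clearly biased towards eltrombopag.* At month 12 rescued controls may also be on drug. With the 60–70% response rate quoted in the Background as an assumption, 30 to 40 of 100 controls could be non-responders at month 6, so the direction at month 12 is open.
- *That sections 8.1.1.3 and 8.11.1 contradict each other on stopping.* They concern different patients in different arms.
- *That the fall in platelets after stopping, described in section 8.3.1, proves dependence here.* That warning is drawn from ITP.

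Off-protocol eltrombopag is also no longer supplied (8.1.1.3, 8.8), which may keep numbers small. Section 12.3 leaves further detail to an SAP that is not at hand, but the classification rule itself is fixed in the protocol.

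**Conclusion.** The point holds in limited form. The section 9.2 rule does not consider eltrombopag, its relapse condition is undefined, and at least one restart route (a haemoglobin fall within PR) passes that condition on either definition. Such a patient, if continued on eltrombopag outside the protocol and weaned off CsA, would be reported as CsA-independent at 24 months.

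The in-protocol second course matters for the 15-month classification and only marginally for the 18-month one. The effect at 24 months rests wholly on off-protocol use, whose frequency is unknown; each such patient adds 1 point in an arm of 100. The endpoint is secondary and descriptive, and the 3-month primary endpoint is untouched. This is a cheap improvement to a definition and no threat to the trial's main conclusion.

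**What to change.** - In section 9.2 and endpoint 11, do not count as CsA-independent a responder who is receiving eltrombopag or other AA-specific treatment at the assessment. Alternatively, report the CsA-independent rate by arm both with and without such patients.
- Take this status from the concomitant-medication record, which Appendix 2 schedules at every visit to month 24, and confirm that the CRF captures off-protocol eltrombopag there.
- State whether the relapse condition in section 9.2 uses the definitions in section 8.1.1.3 or the one in section 9.3.
- A split of the late CR and PR rates by eltrombopag status may be added as a supplementary table. The as-randomised comparison should remain the main one.

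The cost is wording and one extra tabulation. The eltrombopag arm's CsA-independent rate may come out slightly less favourable. None of this proposes a rule on whether or how long eltrombopag may be continued.
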